4.3.8.6. Vital Signs (Pulse and BPr) and Weight

For the primary analysis and any subsequent analysis only data collected before starting further cancer therapy will be summarised.

Percentage change from baseline for pulse, BPr and weight will be summarised by treatment group and visit.

4.3.8.7. Physical Examination

Abnormalities identified from physical examination will be listed.

For the primary analysis and any subsequent analysis only data collected before starting further cancer therapy will be summarised. For each physical examination body system, the number and percentage of patients with abnormalities at baseline and post-baseline will be summarised.

4.3.8.8. ECG

All ECG data received will be presented in data listings.

For the primary analysis and any subsequent analysis only data collected before starting further cancer therapy will be summarised.

QTc summaries will be presented for patients in the full analysis set.

The following ECG parameters will be summarised (absolute values and change from baseline) by visit: QTcF, RR, PR, QRS and QT.

Plots of mean observed QTc parameters and change from baseline in QTc parameters versus time will be presented. Shift plots of the maximum change from baseline versus the baseline value for QTcF, with reference lines for 450 ms, ± 30 ms and ± 60 ms change will be presented.

QTc outliers are defined as QTcF values following dosing that are greater than 450 ms or are increases from baseline greater than 30 ms. QTcF outliers will be highlighted in the data listings and summarised using the following categories:

- Values >450 ms, >480 ms., >500 ms.,
- Increase from baseline of >30 ms., Increase from baseline of >60 ms., Increase from baseline of >90 ms.,
- Values >450 ms and increases of >30 ms. Values >500 ms and increases of >60 ms.

The number and percentage of patients who meet the ECG outlier criteria at any assessment post-date of first dose will be summarised.

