8.3.2 Safety analysis set

The safety analysis set (SAS) will consist of all patients who received at least one dose of study treatment. Safety data will not be formally analysed but summarised using the safety analysis set, according to the treatment received; i.e., erroneously treated patients (e.g., those randomised to treatment A but actually given treatment B) will be summarised according to the treatment they actually received.

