2. ANALYSIS SETS

2.1. Definition of Analysis Sets

2.1.1. Full Analysis Set

The full analysis set (FAS) will include all randomised patients.

The FAS will be used for all demographic summaries and efficacy analyses, and treatment groups will be compared on the basis of randomised study treatment, regardless of the treatment actually received.

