2.1.2. Safety Analysis Set

The safety analysis set will consist of all patients who received at least one dose of study treatment.

Safety data will not be formally analysed but summarised using the safety analysis set, according to the treatment received; i.e. erroneously treated patients (e.g. those randomised to treatment A but actually given treatment B) will be summarised according to the treatment they actually received. If a patient received both treatments, then they will be summarised according to the active treatment.

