4.2.1. Baseline Measurements and Change from Baseline Variables

In general, for summaries using the full analysis set, the last observed measurement prior to randomisation will be considered the baseline measurement. However, if an evaluable assessment is only available on the day of randomisation then this assessment will be used as baseline and assumed to have occurred prior to first dose. For summaries using the safety analysis set the last observation prior to the first dose of study treatment will be considered the baseline measurement unless otherwise specified.

For assessments on the day of first dose where time is not captured, a nominal pre-dose indicator, if available, will serve as sufficient evidence that the assessment occurred prior to first dose.

Assessments on the day of first dose where neither time nor a nominal pre-dose indicator are captured will be considered prior to first dose if such procedures are required by the protocol to be conducted before first dose.

In all summaries, change from baseline variables will be calculated as:

$$\text{post-treatment value} - \text{baseline value} .$$

The percentage change from baseline will be calculated as:

$$\frac{(\text{post-baseline value} - \text{baseline value})}{\text{baseline value}} \times 100.$$

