4.3.8. Safety and Tolerability

The safety analysis set will be used for all safety and tolerability tables, figures and listings except where expressly noted.

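### SAP 4.3.8.8 summarises QTc on the full analysis set as randomised, an unexplained departure from the safety-set rule in Protocol 8.3.2 and SAP 2.1.2

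*SAP*

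**What the plan says.** **Analysis set for safety data.** Protocol 8.3.2 states: "Safety data will not be formally analysed but summarised using the safety analysis set, according to the treatment received". SAP 2.1.2 repeats this and adds a tie-break: "If a patient received both treatments, then they will be summarised according to the active treatment". Neither section carries an exception. SAP 4.3.8 is looser: "The safety analysis set will be used for all safety and tolerability tables, figures and listings except where expressly noted".

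**QTc.** SAP 4.3.8.8 says "QTc summaries will be presented for patients in the full analysis set". The sentence names QTc only. The by-visit summary in the same section covers QTcF, RR, PR, QRS and QT.

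**What the full analysis set is for.** SAP 2.1.1 says "The FAS will be used for all demographic summaries and efficacy analyses", and that "treatment groups will be compared on the basis of randomised study treatment, regardless of the treatment actually received".

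**Baseline.** SAP 4.2.1 ties the baseline to the set. In general, "for summaries using the full analysis set, the last observed measurement prior to randomisation will be considered the baseline measurement". There is a fallback: "if an evaluable assessment is only available on the day of randomisation then this assessment will be used as baseline". For the safety analysis set, baseline is the last observation before first dose. SAP 3.3.7 admits only digital ECGs as baseline.

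**Declared changes.** SAP section 6 lists one change of analysis set from the protocol. It moves the PK set from the full analysis set to the safety set, so that PK can be read by treatment actually received. The QTc choice is not listed.

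**The concern.** QT change is a recognised potential effect of the drug (Protocol 6.9.5), so QTc tables are a part of the safety report that readers will check. On the full analysis set, a patient given the wrong drug is counted for QTc under the randomised arm but for adverse events under the drug received. The choice runs in the opposite direction to the PK change that section 6 does declare, and it is made without a reason.

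The choice also has a side effect through SAP 4.2.1, because naming a set selects a baseline rule. For some patients, increases above 30, 60 and 90 ms would be counted from an ECG further from first dose than the one available.

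**Working it through.** The plan states no figure to reproduce. The check sets the rules side by side, with one small calculation for scale.

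**1. Set and attribution**

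| Source | Set | Attribution |
|---|---|---|
| Protocol 8.3.2 | Safety | Treatment received |
| SAP 2.1.2 | Safety | Treatment received; active if both |
| SAP 4.3.8 | Safety unless expressly noted | As SAP 2.1.2 |
| SAP 4.3.8.8, QTc | Full | As randomised (SAP 2.1.1) |
| SAP 4.3.8.8, RR, PR, QRS, QT | Not named, so safety by default | Treatment received |

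SAP Table 1 confirms the practical difference: an incorrectly dosed patient is analysed as randomised in the full analysis set and as treated in the safety set. Open-label osimertinib after recurrence does not add to this, because 4.3.8.8 summarises only data from before further cancer therapy.

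**2. QTcF and its components.** SAP 3.3.7 derives QTcF as QT divided by the cube root of RR. On the literal reading, the derived value sits on one set while QT and RR sit on another, within the same by-visit summary.

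**3. When the baselines differ.** The inputs are:
- Protocol Table 1 schedules ECGs at screening (Day -28 to Day -1) and pre-dose on Day 1.
- Footnote i exempts screening ECGs from digital collection.
- Protocol 5.2.3 bars a non-digital screening ECG from being the baseline and then requires a digital one at the baseline visit.
- Footnote a lets a screening assessment done within 14 days stand without a Day 1 repeat if the patient's condition has not changed.

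| ECGs available | Full-set baseline | Safety-set baseline | Differ? |
|---|---|---|---|
| Non-digital screening, digital Day 1 pre-dose | Day 1 (fallback) | Day 1 | No |
| Digital screening, no Day 1 repeat | Screening | Screening | No |
| Digital screening and digital Day 1 pre-dose | Screening | Day 1 | Yes |

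This takes *before randomisation* at the level of the day, as the fallback clause implies. Only the third row is affected. The documents do not give its frequency.

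**4. Denominator.** SAP 4.3.8.8 defines outliers on values after dosing, so an undosed patient can never be in a numerator. No denominator is stated. If all patients in the full analysis set were used, the relative dilution would be u/N, where u is the number undosed. Protocol 1.4 gives N = 339 (osimertinib) and N = 343 (placebo). The documents do not give u; I assume 0 to 5 per arm.
- u = 0: no effect.
- u = 5: 5/339 = 1.5% and 5/343 = 1.5%, relative.
- Illustration: a rate of 10% among dosed osimertinib patients would read 10% × 334/339 = 9.85%.

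**The case against.** The strongest reply is that SAP 4.3.8 permits express exceptions and that the QTc sentence is one. It is not alone: SAP 4.3.8.3 puts the deaths summary on the full analysis set. This stands as far as it goes. There is no breach of 4.3.8, and it would be wrong to say that QTc differs from every other safety table. But the exception clause does not appear in Protocol 8.3.2 or SAP 2.1.2, and section 6 neither lists nor explains the departure.

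Three stronger readings are tempting, and the documents do not support them.

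- *The QTc baseline contravenes the protocol's safety-set rule.* Protocol 8.3.2 fixes population and attribution only. The baseline difference arises wholly within SAP 4.2.1.
- *Every patient, or every patient with a digital screening ECG, gets an older baseline.* The digital-only rule, the screening exemption, the 14-day no-repeat footnote and the randomisation-day fallback remove many possible cases. Protocol 3.2 bases QTc eligibility on the screening clinic's own machine reading, which also fits screening ECGs often being non-digital.
- *Never-dosed patients enter the QTc percentages.* SAP 4.3.8.8 states no denominator. SAP 4.3.8.9 does state one for LVEF (patients with a baseline and at least one later value), so the QTc rule is open rather than known.

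It is also fair that attribution matters only if some patients received the wrong drug, and the documents report no such count.

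**Conclusion.** The point holds as an inconsistency of small size. The analysis set for QTc conflicts with Protocol 8.3.2 and SAP 2.1.2, is unexplained, and is missing from SAP section 6. On a literal reading it also splits QTcF from QT and RR.

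The effect on results is limited to three routes: patients given the wrong drug (number not stated), patients with digital ECGs both before the day of randomisation and pre-dose on Day 1 (number not stated, baseline only), and the denominator (at most about 1.5% relative, resting on the assumed 0 to 5 undosed patients per arm and on use of the full randomised count). Nothing in the documents shows that any QTc conclusion would change, or in which direction a baseline shift would act.

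**What to change.** In SAP 4.3.8.8, replace *full analysis set* with *safety analysis set*. QTc is then summarised by treatment received, and SAP 4.2.1 together with SAP 3.3.7 gives the last digital ECG before first dose as baseline, consistent with the other ECG parameters. If the full analysis set was intended, the alternative is to list the departure in SAP section 6 with its reason.

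The text change is a single word and needs no new data. If QTc tables have already been produced on the full analysis set, they would have to be rerun. SAP section 7 foresees further safety reporting, so the correction still has use.

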4.3.8.9. Left Ventricular Ejection Fraction

For the primary analysis and any subsequent analysis only data collected before starting further cancer therapy will be summarised.

LVEF outliers are defined as LVEF values following dosing that are:

- ≥ 10 percentage points decrease from baseline and $<50\%$, or
- ≥ 15 percentage points decrease from baseline and $\geq 50\%$.
- LVEF outliers and abnormal values will be highlighted in the data listings and summarised.

Percentages will be calculated for patients with a baseline and at least one post baseline measurement.

Patients with outliers that are associated with an AE (related or unrelated to study treatment) will be listed and summarised as appropriate, along with the duration of the abnormality.

4.3.8.10. WHO Performance Status

For the primary analysis and any subsequent analysis only data collected before starting further cancer therapy will be summarised.

WHO performance status will be listed and summarised as the frequency and percentage of patients by treatment and visit for the safety analysis set.

4.3.8.11. Ophthalmologic Assessment

Ophthalmologic assessment will be listed by treatment and visit for the safety analysis set.

4.3.9. PK Concentration Data

All plasma concentrations of AZD9291 and metabolites (AZ5104 and AZ7550) will be listed for the PK analysis set.

The following summary statistics will be presented for AZD9291, AZ5104 and AZ7550 plasma concentrations and metabolite(s) to AZD9291 ratio by treatment day and nominal sample time window for the PK analysis set:

- Geometric mean (gmean) calculated as e^{μ} , where μ is the mean of the data on a logarithmic scale. The corresponding error bars will be calculated as $\exp(\mu \pm s)$ and referred to as $Gmean \pm StdDev$ in the table
- Geometric standard deviation (GeoSD) calculated as e^s , where s is the standard deviation of the log transformed data
- Coefficient of variation (CV) calculated as $100 \times \sqrt{\frac{\exp(s^2) - 1}{\exp(s^2) + 1}}$
- Arithmetic mean calculated using untransformed data
- Standard deviation (StdDev) calculated using untransformed data
- Minimum
- Median
- Maximum
- Number of observations (n)
- $n \leq LLOQ$

Non-quantifiable (NQ) values of plasma concentrations will be handled as follows:

- If, at a given time point, 50% or less of the plasma concentrations are NQ, the gmean, CV, $gmean \pm StdDev$, arithmetic mean and StdDev will be calculated by substituting the limit of quantification (LOQ) for values which are NQ.
- If more than 50%, but not all, of the concentrations are NQ, the gmean, CV, $gmean \pm StdDev$, arithmetic mean and StdDev will be reported as not calculable (NC).
- If all the concentrations are NQ, the gmean and arithmetic mean will be reported as NQ and the CV, $gmean \pm StdDev$ and StdDev as NC.
- The number of values above LLOQ will be reported for each time point along with the total number of collected values.

If data are available for less than three patients, no summary statistics other than minimum, maximum and n will be presented.

The concentration data for Cycle 1 Day 1 and Cycle 3 Day 1 may be displayed graphically for the PK analysis set, as appropriate. Displays may include plasma concentration profiles versus time and gmean concentrations (\pm StdDev) both on the linear and on the log-scale versus time, as appropriate.

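### The CV formula printed in SAP 4.3.9 carries a spurious denominator exp(s²)+1; programmed as written, every CV reported for PK concentrations is at least 29% too low and cannot reach 100%

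*SAP*

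**What the plan says.** SAP 4.3.9 sets out the descriptive statistics for plasma concentrations of AZD9291, AZ5104 and AZ7550 and for the metabolite-to-parent ratios, by treatment day and sampling window, in the PK analysis set. One line reads "Coefficient of variation (CV) calculated as", followed by 100 times the square root of a fraction. In the extracted text the numerator and denominator appear as "\exp(s^2) - 1}{\exp(s^2) + 1". The symbol s is defined one line earlier, in the item "Geometric standard deviation (GeoSD) calculated as" e to the power s, "where s is the standard deviation of the log transformed data".

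The same list asks for other measures of spread that do not use the CV expression:
- the geometric SD;
- geometric-mean error bars at exp(μ ± s);
- "Standard deviation (StdDev) calculated using untransformed data";
- the minimum and maximum.

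Protocol 8.4.3 says that concentrations will be listed and summarised in the CSR but gives no CV formula. The SAP is therefore the only specification of the CV in these documents.

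**The concern.** The section works on the log scale throughout, and the CV that matches a log-scale SD s is 100 × sqrt(exp(s²) − 1). Dividing by exp(s²) + 1 inside the root gives a different quantity that has no interpretation as SD over mean.

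PK characterisation is a secondary objective (Protocol 2.2, SAP 1.1), and these tables go into the CSR. Programmed as printed, the CV column would show less between-patient variability than there is, and the gap would widen as the analyte becomes more variable. The table would also contradict itself, because the geometric SD beside it would imply a larger CV. Protocol 8.4.3 and SAP 3.4 allow these data to be combined with those of other studies, so a reader could well compare this CV with one calculated correctly elsewhere.

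**Working it through.** **Inputs.** From SAP 4.3.9: the printed CV formula and the definition of s. The documents give no value of s and no numerical CV, so there is no stated figure to reproduce. The s values below are assumptions chosen to show the range.

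**Correct expression.** If log concentration is normal with mean μ and SD s, then
- mean = exp(μ + s²/2);
- variance = (exp(s²) − 1) × exp(2μ + s²);
- CV = 100 × SD/mean = 100 × sqrt(exp(s²) − 1).

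**Ratio of printed to correct.**
sqrt((exp(s²) − 1)/(exp(s²) + 1)) ÷ sqrt(exp(s²) − 1) = 1/sqrt(exp(s²) + 1).
For any s > 0, exp(s²) + 1 is greater than 2, so the ratio is below 1/sqrt(2) = 0.707. The relative shortfall is at least 1 − 0.707 = 0.293, that is 29%.

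**Ceiling.** (exp(s²) − 1)/(exp(s²) + 1) = tanh(s²/2), which is always below 1. The printed CV therefore cannot reach 100%, whereas a true CV has no such limit.

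**Small-s check.** A log-scale SD of 0.1 should give a CV close to 10%. The correct formula gives 10.0% and the printed one 7.1%.

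**One case in full, s = 0.5.** exp(0.25) = 1.2840.
- Printed: 100 × sqrt(0.2840/2.2840) = 35.3%.
- Correct: 100 × sqrt(0.2840) = 53.3%.

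| assumed s | geometric SD, e^s | CV as printed | correct CV | ratio |
|---|---|---|---|---|
| 0.2 | 1.22 | 14.1% | 20.2% | 0.700 |
| 0.3 | 1.35 | 21.2% | 30.7% | 0.691 |
| 0.5 | 1.65 | 35.3% | 53.3% | 0.662 |
| 0.6 | 1.82 | 42.2% | 65.8% | 0.641 |
| 0.833 | 2.30 | 57.7% | 100.0% | 0.577 |
| 1.0 | 2.72 | 68.0% | 131.1% | 0.519 |
| 1.5 | 4.48 | 90.0% | 291.3% | 0.309 |

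Simulation of 4 million log-normal values per s gave CVs of 30.7% at s = 0.3, 53.2% at s = 0.5 and 131.2% at s = 1.0. These agree with the correct column, not the printed one.

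**Consistency within the table.** The correct CV can be recovered from the geometric SD as 100 × sqrt(exp((ln GeoSD)²) − 1). A reported geometric SD of 1.65 implies about 53%, while the CV beside it would read 35%.

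**The case against.** The strongest objection is that the whole point rests on one typeset fraction read from a PDF by a program. There is no worked example and no second statement of the formula to confirm it. Other formulas in these documents also look unreliable. SAP 4.3.7.1 shows the hazard ratio as exp(U/sqrt(V)) where Protocol 8.5.1 has exp(U/V), and the interval in Protocol 8.5.1 divides 1.96 by sqrt(V) in one limit and multiplies in the other. Whether these are authoring or conversion slips cannot be told from the text. This objection stands to the extent that the source must be checked before the SAP is called wrong. It does not remove the point: the neighbouring expressions in the same list read correctly, and nothing in either document gives a different CV formula.

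A second objection is that little depends on this number, and that too stands. The CSR output is descriptive and PK is outside the testing hierarchy. Population PK modelling works from the concentration data under a separate plan (SAP 3.4), and nothing says that it uses this CV.

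A reader might also infer that all reported PK variability is understated, or that the CV is wrong at every time point. The documents support neither. The other measures of spread in SAP 4.3.9 do not use the formula. The CV itself is reported as not calculable where more than half of the values are non-quantifiable, and it is not presented where fewer than three patients have data.

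**Conclusion.** The CV formula as printed is wrong. If it is in the source SAP and was programmed, every CV that is reported under SAP 4.3.9 is at least 29% too low in relative terms and is capped below 100%. The shortfall grows with s: about 31% at s = 0.3, 34% at s = 0.5 and 48% at s = 1.0 (one minus the ratios above). These s values are assumed. The 29% bound and the 100% ceiling hold for any s above zero.

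The effect is confined to one line of a descriptive PK table. The other measures of spread in that table are unaffected, and no DFS, OS, alpha or sample-size result depends on the CV. The documents do not show that any reported CV is in fact wrong, because they contain no CV result and the denominator may be a PDF-reading artefact. This is an inexpensive correction to a secondary-objective output and does not threaten the trial's conclusions.

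**What to change.** 1. Compare the formula with the source SAP file and with the program that produces the PK tables.
2. If the denominator is there, replace the line with CV = 100 × sqrt(exp(s²) − 1), s being the SD of the natural-log concentrations.
3. Correct any CV already tabulated. SAP 7 places the primary-reporting analyses at the January 2020 cut-off, and Protocol 1.4 reports results from that cut, so PK tables may already exist and a change to the SAP alone would not repair them. Each value can be checked against the geometric SD in the same table.

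If the denominator turns out to be a conversion artefact, no change is needed. Otherwise the cost is one line of SAP text, one line of code and a rerun of the PK summary tables.

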5. INTERIM ANALYSES

An Independent Data Monitoring Committee (IDMC) will be convened and will meet every six months for the first two years from the first patient randomised, and yearly thereafter. Further meetings for review of safety data may be convened at the discretion of IDMC. The IDMC will review safety assessments and make recommendations to continue, amend, or stop the study based on safety findings. Serious adverse events, adverse events, and other safety data will be reviewed, and individual and aggregated safety data will be evaluated by the IDMC.

The IDMC will conduct a futility analysis. Further details will be documented in the IDMC Charter prior to the first DMC safety review meeting. The IDMC will review the futility outcomes and provide a recommendation for whether the study should continue, stop or be modified in some way.

